2.2. Study Design

Overview of Study Design and Key Features				
	Placebo: 20ml sterile saline			
	 Dose: N/A 			
	 Route: Intravenous 			
	 Regimen: Weeks 0, 2, 6, and 10. 			
	• Duration of administration: 1 hour			
	• Study treatment details,			
	Placebo HB-adMSCs (allogencic)			
	Manufacturer Baxter or an equivalent manufacturer Hope Biosciences			
	Dosage 20 ml sterile saline $2 \times 10^{-8} \pm 20\%$ cells			
	suspended in 20 ml sterile saline			
	Route Intravenous Intravenous			
	Administration Rate 4-5 ml/min 4-5 ml/min			
	Syringe will contain 20 ml of Syringe will contain 20 ml of			
	Preparation sterile saline. allogeneic HB-adMSCs. Placebo should be diluted in 250 ml of 0.9% Sodium chloride. HB-adMSCs should be diluted in 250 ml of 0.9% Sodium chloride.			
Study	• Participants will be randomised 1:1 to receive HB-adMSCs active			
Intervention	treatment or Placebo.			
Assignment				
Interim	No interim analysis planned			
Analysis				

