3.2. Interim Analysis

No interim analysis planned.

Population	Definition / Criteria	Analyses
		Evaluated
Safety analysis set	 All randomized subjects who received at least one dose of HB-adMSCs infusion or placebo. If participants receive a treatment different to their randomized treatment, they will be analysed according to the treatment actually received. 	 Safety Study Population
Efficacy analysis set	 All randomized participants who received all 4 infusions of HB-adMSCs or placebo. Participants will be analysed according to their randomized treatment. 	• Efficacy
Screened Population	 This population consists of all subjects who signed an ICF to participate in the clinical trial. This population will be used for summarizing screening failures and reasons for screening failures. 	Study Population

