To further evaluate if the improvements are clinically relevant, effect size of the treatment difference at Week 2, Week 6, Week 10, Week 14, Week 20 and Week 26 will also be calculated for the efficacy endpoint VAS score using cohen's d calculation. Cohen's d is a standardized measure of effect size (ES) that provides information on the amount of change in the outcome meaure relative to the variation within the measure. Cohen's d is calculated as the difference between the HB-adMSCs mean score and Placebo mean scores divided by the standard deviations of the scores. An absolute effect size of <0.2 will be considered trivial, ≥ 0.2 as small, ≥ 0.5 as medium and >0.8 as large ^[1].

Cohen's d = $\frac{M1-M2}{(sd1+sd2)/2}$, where M1 and M2 are the Mean scores for HB-adMSCs and Placebo respectively, and SD1 and SD2 are the corresponding standard deviations.

Table 1 Established MCID values for the outcome measures.

Outcome measure	MCID
VAS (Pain)	-1.9 [2]

MCID will be calculated as the mean change from baseline, to compare the result with the reference values established in the literature (provided in Table 1) for ΔVAS Score. Clinically important improvements for VAS score will be defined as mean change from baseline \geq established (published) MCID.

Results presentation

Secondary endpoints will be summarized using n, mean, confidence interval of mean, SD, median, minimum and maximum. And p-value for paired comparison will be displayed for all post-baseline visits.

Normality checking

Distribution assumptions used for the statistical analysis will be examined by obtaining a normal plot and Shapiro-Wilk Test.

Non-parametric analyses, Wilcoxon signed-rank test will be conducted if the normality assumption does not hold.

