6. SAMPLE SIZE DETERMINATION

The sample size consists of 80 subjects who have been diagnosed with Chronic Post-COVID-19 - Syndrome.

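### The SAP's small cut-off for Cohen's d (0.2) lies below the standard error of d at 40 per arm (0.224), so an unadjusted d with no interval earns a non-trivial label about 37% of the time when there is no effect.

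*SAP*

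**What the plan says.** Under Additional analysis, SAP 5.2.2 first ties clinical significance to a published MCID of -1.9, applied to mean change from baseline. It then adds Cohen's d for the treatment difference at Weeks 2, 6, 10, 14, 20 and 26, with the purpose "To further evaluate if the improvements are clinically relevant".

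The definition is "Cohen's d is calculated as the difference between the HB-adMSCs mean score and Placebo mean scores divided by the standard deviations of the scores". The formula that follows subtracts M2 from M1 and divides by the simple average of the two SDs, "where M1 and M2 are the Mean scores for HB-adMSCs and Placebo respectively, and SD1 and SD2 are the corresponding standard deviations". These are arm means, not the LSMeans of the planned models.

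The grading begins "An absolute effect size of <0.2 will be considered trivial" and continues with small from 0.2, medium from 0.5 and large above 0.8. No interval is specified for d. For the model-based mean differences, SAP 5.1.1 and 5.2.2 do plan 95% confidence intervals and p-values.

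On numbers, SAP 6 says only "The sample size consists of 80 subjects", SAP 2.2 says "Participants will be randomised 1:1 to receive HB-adMSCs active", and the efficacy analysis set is "All randomized participants who received all 4 infusions of HB-adMSCs or placebo".

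**The concern.** The labels are meant to help a reader judge whether an improvement matters. A label does that only if noise seldom produces it. Here the lowest non-trivial cut-off is smaller than the sampling error of the statistic being graded, and no interval is planned that would show this.

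Two further choices make it worse. The arm means are unadjusted although the same section fits models with baseline and the stratification factors. The label also ignores direction, so a difference favouring placebo is graded like one favouring HB-adMSCs.

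What is at stake is the wording of the study report: a small effect could be offered in support of clinical relevance when the data are compatible with none.

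**Working it through.** The documents give no power, SD or error rate for d, so there is no plan figure to reproduce.

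**Inputs**
- N = 80 (SAP 6), randomised 1:1 (SAP 2.2), so n = 40 per arm if everyone is analysed. The efficacy set requires all four infusions and no dropout rate is given, so 40 is an assumption and an upper limit.
- Cut-offs 0.2, 0.5 and 0.8 on the absolute value (SAP 5.2.2).
- True difference zero, normal data, equal SDs (assumptions).
- Visits with VAS after baseline: Weeks 2, 6, 10 and 26. Weeks 14 and 20 are phone calls, and the protocol's schedule of assessments lists no VAS there.

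**Standard error of d with no effect**
- SE = sqrt(2/n) = sqrt(2/40) = 0.224, which is above 0.2.

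**Chance of a label at one visit**
- Small or larger: 0.2/0.224 = 0.894. The two-sided tail is 37.1% (normal) or 37.4% (t, 78 df). Simulation with the SAP's own formula gives 37.5%.
- Small or larger in the direction favouring HB-adMSCs: 18.7% (simulation), half of the above.
- Medium or larger: 0.5/0.224 = 2.236, giving 2.5% (normal) or 2.8% (t).
- Above 0.8: under 0.1%.

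**Fewer subjects in the efficacy set (assumed, t distribution)**

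| n per arm | P(absolute d at least 0.2) |
|---|---|
| 40 | 37.4% |
| 36 | 39.9% |
| 32 | 42.7% |
| 30 | 44.2% |

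**What an interval would show**
- At d = 0.20, SE = sqrt(2/40 + 0.04/160) = 0.2242, so the 95% CI is 0.20 ± 1.96 × 0.2242 = -0.24 to 0.64.
- Two-sided p < 0.05 needs an absolute d of about 1.991 × 0.2236 = 0.445.

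**What adjustment would do**
- Adjusted difference over the SD of scores: SE = 0.224 × sqrt(1 - r²), with r the assumed correlation between baseline and follow-up. The chance of small or larger falls to 34.8% (r = 0.3), 30.2% (r = 0.5) or 21.0% (r = 0.7).
- Adjusted difference over the SD of changes: SE = 0.224 × sqrt((1 + r)/2). At r = 0.7 this is 0.206, so 0.2/0.206 = 0.97 and the chance is about 33%. The gain therefore depends on which SD is used, which is why the SAP must name it.

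**The case against.** Several stronger readings are tempting, and the documents do not support them.

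- **That the SAP grades clinical relevance from d alone.** It does not. The MCID is named first, and d is a further evaluation under Additional analysis. As written, though, the MCID applies to mean change from baseline. That leaves d as the only planned relevance measure that compares the arms.
- **That every feature of the definition contributes to the 37%.** The rate comes mainly from sample size against a cut-off of 0.2. The missing interval hides the rate but does not change it. The averaged SD is immaterial: with equal SDs the simulated rate is 37.5%, against 37.4% with a pooled SD. Even at assumed SD ratios of 1.5 and 2 it is 38.3% against 37.2%, and 40.0% against 37.5%. Nothing in the documents suggests such ratios.
- **That direction is lost.** The formula is signed, HB-adMSCs minus placebo. Only the label uses the absolute value.
- **That one label at any visit is enough.** The SAP states no such rule, so a rate over several visits would test a criterion it does not contain.
- **That baseline imbalance certainly enters d.** The endpoint is change from baseline, and the mean scores could be read as mean changes. The text does not settle this. With changes in both numerator and denominator the SE is still sqrt(2/n), so the 37% is unaltered.

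It is also fair to say that a reader would see the model-based difference with its 95% CI beside the label. That reduces the risk of misreading. It does not remove it, because the label is attached to a different, unadjusted quantity, and the SAP does not say how to read a small label when the adjusted interval spans zero.

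**Conclusion.** The concern holds in a limited form. With 40 analysed per arm and no treatment effect, a label of small or larger is expected about 37% of the time at a single visit with VAS data, about half of that in the favourable direction. The per-visit rate is higher if fewer subjects complete all four infusions. The excess is almost entirely small labels, with medium or larger under 3%.

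The figures assume normal data and equal SDs. The adjusted rates also depend on an assumed baseline correlation. The primary test and its error rate are untouched. What needs correcting is how a descriptive effect size may be used to support a statement about clinical relevance.

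**What to change.** In the Cohen's d paragraph of SAP 5.2.2:

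1. Take the numerator from the adjusted HB-adMSCs minus placebo difference already planned: the ANCOVA at Week 26 and the repeated-measures model at the earlier visits with VAS data.
2. State the denominator, saying whether it is the SD of scores or of changes. The averaged SD may stay.
3. Report d with its sign and a 95% CI, and name the method. Dividing the limits of the adjusted interval by the SD is adequate for small effects: in the unadjusted case at d = 0.20, allowing for error in the SD moves the SE only from 0.2236 to 0.2242.
4. State that a small label alone is not evidence of clinical relevance.

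There is no need to withhold labels until the interval excludes zero. That would turn a descriptive measure into a second significance test and leave most of the small band unusable.

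The cost is a few lines of SAP text and minor extra programming. The sponsor should expect fewer apparent non-trivial effects.

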3. STATISTICAL HYPOTHESES

The primary analysis will test whether HB-adMSCs is superior to Placebo according to the following statistical hypotheses:

Null hypothesis H0: The difference in change from baseline to Weeks 26 in Visual Analog Scale of Neurological Symptoms score between treatment groups (HB-adMSCs – Placebo) is equal to zero.

Alternative hypothesis H1: The difference in change from baseline to Weeks 26 in Visual Analog Scale of Neurological Symptoms score between treatment groups (HB-adMSCs – Placebo) is not equal to zero.

Secondary analysis will be tested for mean difference for change from Baseline to Week 26 for efficacy endpoints for both treatment groups,

Null hypothesis H0: $\Delta = 0$ Alternative hypothesis H1: $\Delta \neq 0$

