5.1.1. General Methodology

Unless otherwise stated, all hypotheses will be tested at a 2-sided significance level of 0.05 and 95% confidence interval. All continuous measurements will be summarised descriptively at each visit by treatment using observed data.

Summary of continuous variables will be presented using N, Mean, 95% confidence interval of mean, Standard Error of mean (SE), Standard Deviation (SD), Median and Range (Minimum and Maximum). The categorical variables will be presented using number and percentage based on N.

For measurements over time mean values will be plotted to explore the trajectory over time. Observed data will be used as the basis for plotting data along with bars as +/- SE, not otherwise specified.

As a primary analysis, a standard Analysis of Covariance (ANCOVA) will be applied for primary and secondary endpoint to test the significance of the effects of the treatment at Week 26. The model includes treatment as fixed factor and the corresponding baseline value as a covariate.

A parametric Repeated Measures Analysis (RMA) Model will be applied as a secondary analysis to test the significance of the effects of the treatment at Week 2, Week 6, Week 10, Week 14, Week 20 and Week 26 including baseline as covariate.

Presentation of results from a statistical analysis model will include the estimated mean treatment effects (Least Square Means (LSMeans)). For all endpoints analysed statistically, estimated mean treatment differences will be presented together with two-sided 95% confidence intervals and p-values,

HB-adMSCs - Placebo

Pairwise t-test will be performed on the efficacy endpoints to test the difference between baseline and week 26 (EOS) as secondary analysis. Data for all the efficacy outcomes will be checked for normality (Shapiro-Wilk Test).

When there is a larger deviation of data distribution from normality, appropriate nonparametric test will be used.

Study population analyses including analyses of subject disposition, demographic and baseline characteristics, medical history, prior and concomitant medications.

Disposition summary includes, subject screened, randomized and disposition at end of study – Week 26 along with reasons for withdrawals. Subjects in different analysis populations also will be presented.

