 - Stratification: pre-existing condition to COVID-19 (Y/N), average VAS score of Neurological Symptoms (<5cm/>=5cm), and age group (<43/>=43)
- Furthermore, the model will include:

- Interaction terms between treatment and visit
- And Interaction terms between baseline and visit
- Subject will be included as a random factor

Model Checking and Diagnostics

For the Repeated Measures Analysis (RMA) Model assumptions will be checked, and appropriate adjustments may be applied based on the data.

Distribution assumptions underlying the model used for analysis will be examined by obtaining a normal probability plot of the residual and a plot of the residuals versus the fitted values (i.e., checking the normality assumption and constant variance assumption of the model respectively) to gain confidence that the model assumptions are reasonable.

Non-parametric analyses, Mann-Whitney U (or Wilcoxon Rank-Sum) Test will be conducted if the normality assumptions does not hold.

Results presentation

Presentation of results from a statistical analysis model will include the estimated mean treatment effects (Least Square Means (LSMeans)) and estimated mean treatment differences will be presented together with two-sided 95% confidence intervals standard error for mean difference and p-value.

Additional analysis

Summary analysis method

To compare difference between baseline to Week 2, Week 6, Week 10, Week 14, Week 20 and Week 26, a paired t-test will be used for primary endpoint change from baseline VAS to check the statistical significance. Clinical significance will be determined using the established (published) MCID value for the VAS change from baseline. The available MCID value for Change from baseline VAS measure is provided in the Table 1 which will be used as a threshold to evaluate/identify clinically relevant changes.

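### SAP 5.2.2 prints its rule for clinically important VAS improvement with the inequality the wrong way round, and once repaired the rule still measures change from baseline, not treatment effect

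*SAP*

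**What the plan says.** The rule stands in SAP 5.2.2 under Additional analysis. It opens: "Clinical significance will be determined using the established (published) MCID value for the VAS change from baseline". The Table 1 value is one "which will be used as a threshold to evaluate/identify clinically relevant changes". The text goes on: "MCID will be calculated as the mean change from baseline, to compare the result with the reference values established in the literature". The definition follows: "Clinically important improvements for VAS score will be defined as mean change from baseline", then a greater-than-or-equal sign and a reference to the published MCID. Table 1 has one row, labelled VAS (Pain), with the value -1.9. Its source, reference 2 in SAP section 8, is a study of pain VAS in patients after hand surgery.

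The accompanying test is within-subject: "a paired t-test will be used for primary endpoint change from baseline VAS to check the statistical significance". SAP 5.1.1 says likewise: "Pairwise t-test will be performed on the efficacy endpoints to test the difference between baseline and week 26 (EOS) as secondary analysis".

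The trial's question is a comparison of arms. The null hypothesis in SAP section 3 concerns "The difference in change from baseline to Weeks 26 in Visual Analog Scale of Neurological Symptoms score between treatment groups". For that question, SAP 5.2.2 plans an ANCOVA treatment difference with a 95% CI and, as a further look at clinical relevance, Cohen's d for the treatment difference.

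The protocol (Trial Assessments, Visual Analog Scale of Symptoms) sets the scale at 0 to 10 cm, higher being worse.

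**The concern.** There are three linked problems.

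- **Direction.** On a scale where lower is better, a negative MCID and a greater-than-or-equal sign do not describe improvement. The SAP prints no formula for change that would settle the reading.
- **Quantity judged.** Mean change from baseline includes placebo response and natural recovery as well as any treatment effect. It may also include some regression to the mean, because inclusion criterion 4 requires at least one symptom at 5 cm at screening; re-measuring baseline at Week 0 should remove part of that. A rule on this quantity cannot separate the arms.
- **Source of the threshold.** It is a pain value from a surgical population. Of the five neurological items (fatigue, brain fog, headache, sleep, taste/smell), only headache is pain. The SAP gives no reason for carrying the value over.

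At stake is the clinical-relevance statement in the study report. The SAP gives the deciding role to this rule, so the report must either follow a rule that reads wrongly or depart from it without a prespecified alternative.

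**Working it through.** **No figure to reproduce.** The -1.9 is taken from a publication, and SAP section 6 gives only the total of 80, with no SD, effect size or power. The check is therefore one of logic, followed by an illustration on stated assumptions.

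**Step 1: direction.** Let d = follow-up minus baseline, so negative is better. The printed rule is change ≥ MCID. Each row is one reading.

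| MCID | Change taken as | d = -3.0 | d = -1.0 | d = 0 | d = +2.0 |
|---|---|---|---|---|---|
| -1.9 (printed) | follow-up minus baseline | fails | passes | passes | passes |
| -1.9 (printed) | baseline minus follow-up | passes | passes | passes | fails |
| +1.9 | follow-up minus baseline | fails | fails | fails | passes |
| +1.9 | baseline minus follow-up | passes | fails | fails | fails |

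With the printed -1.9, zero change passes under either subtraction. In the second row, worsening also passes up to d = +1.9. Only the last row is a rule for improvement, and it needs both a changed sign and a subtraction order that the SAP does not state. Reading the rule as absolute change ≥ 1.9 excludes zero but counts a 2 cm worsening. Writing d ≤ -1.9 gives the evident intent directly.

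**Step 2: the repaired rule with no treatment effect.** Inputs from the documents: 80 participants (SAP section 6) randomised 1:1 (SAP 2.2), so 40 per arm, and the threshold -1.9. Assumptions not in the documents: SD of change 2.0 to 3.0 cm, a common true mean change μ (varied below), the rule applied arm by arm, and a score on the 0 to 10 cm scale.

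- One arm passes: p = Φ((-1.9 - μ) / (SD/√n))
- Both arms pass: p²
- HB-adMSCs alone passes: p(1 - p)

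Worked case, μ = -2.5, SD = 2.0, n = 40: standard error = 2.0/√40 = 0.316; z = 0.6/0.316 = 1.90; p = 0.971; both = 0.943; HB-adMSCs alone = 0.028.

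| μ | One arm, SD 2 / SD 3 | Both arms, SD 2 / SD 3 | HB-adMSCs alone, SD 2 / SD 3 |
|---|---|---|---|
| -1.0 | 0.002 / 0.029 | <0.001 / 0.001 | 0.002 / 0.028 |
| -1.5 | 0.103 / 0.200 | 0.011 / 0.040 | 0.092 / 0.160 |
| -1.9 | 0.500 / 0.500 | 0.250 / 0.250 | 0.250 / 0.250 |
| -2.0 | 0.624 / 0.583 | 0.389 / 0.340 | 0.235 / 0.243 |
| -2.5 | 0.971 / 0.897 | 0.943 / 0.805 | 0.028 / 0.092 |
| -3.0 | >0.999 / 0.990 | 0.999 / 0.980 | <0.001 / 0.010 |

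The efficacy set is "All randomized participants who received all 4 infusions of HB-adMSCs or placebo", so it may be smaller than 40 per arm. With an assumed 32 per arm and μ = -2.5, both arms pass with probability 0.912 (SD 2) to 0.759 (SD 3), and HB-adMSCs alone with 0.043 to 0.112.

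The result depends almost wholly on μ. With no treatment effect, p(1 - p) peaks at 0.25, when the common mean change sits on the threshold.

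**The case against.** The sentence defines improvements, and neither zero change nor a worsening is one. A sensible analyst would read the rule as a reduction of at least 1.9, and a negative MCID itself suggests follow-up minus baseline. A slip of sign or operator is the likeliest explanation. This stands: a reader might infer that the report will call worsening patients improved, and the documents do not support that forecast. What remains is that the intended rule is not the printed one.

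The SAP states openly that the MCID concerns change from baseline, places it under Additional analysis, and assesses the treatment difference by Cohen's d and the ANCOVA estimate with its CI. So it would be wrong to say that the plan has no between-arm view of clinical relevance. The narrower point survives: clinical significance is assigned to the MCID rule, and neither between-arm measure is tied to it.

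The probabilities rest on an assumed mean. Any single row, such as 80% to 94% at -2.5, would be unrepresentative, hence the range. The SAP also does not say whether the mean is taken by arm or pooled. If it is pooled, the both-arms calculation does not apply, but the rule then compares the arms even less.

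Finally, a reader might infer that 1.9 has never been validated for these symptoms or for group differences. That is a claim about literature outside the documents. They show only where the value comes from and that no justification is given.

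**Conclusion.** The point holds as a correctable flaw in an additional analysis. The printed inequality is wrong on the documents' own scale and value, whichever way change is subtracted; that needs no assumption. With the direction repaired, the rule can still be met when treatment does nothing. Across assumed common mean changes of -1.0 to -3.0 cm and SDs of 2 to 3 cm at 40 per arm, both arms pass with a probability from under 0.1% to 99.9%, and HB-adMSCs alone with up to 25%. Both arms passing may describe each arm correctly, but it carries no information about treatment.

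A reader might infer that the primary result is compromised. It is not: the ANCOVA estimate, its interval and its p-value do not use the MCID. The exposure is limited to what the report says about clinical relevance.

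**What to change.** Amend SAP 5.2.2 as follows.

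1. Define change as follow-up minus baseline and write the criterion as mean change ≤ -1.9, that is, a reduction of at least 1.9. State whether the mean is by arm.
2. Label within-arm MCID and paired t-test results as descriptive.
3. Base any statement on the clinical relevance of treatment on the between-arm difference with its 95% CI, which is already planned.
4. State that 1.9 is a pain VAS value from a postoperative hand-surgery population, and that the SAP does not justify its use for mostly non-pain symptoms or as a between-group benchmark. If the treatment difference is set beside it, show it as a reference only.

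The cost is a few lines of SAP wording and no new analysis. The downside is that clinical-relevance claims become harder to make.
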